## 1. Glossary of Abbreviations

Abbreviation	Description
°C	degrees Celsius
°F	degrees Fahrenheit
ADA	anti-drug antibody
AE	adverse event
AESI	adverse event of special interest
ANCOVA	analysis of covariance
ATC	Anatomical Therapy Chemical
BMI	body mass index
BSA	body surface area
CI	confidence interval
CMC	CarpoMetaCarpal joint
CMH	Cochran-Mantel-Haenszel
CNS	Central Nervous System
COVID-19	Coronavirus Disease 2019
CS	clinically significant
CSH	heterogeneous compound symmetry
CTC	Common Toxicity Criteria
CTCAE	Common Terminology Criteria for Adverse Events
CV	coefficient of variation
DBP	diastolic blood pressure
DECT	dual-energy computed tomography
dL	deciliter
DMC	Data Monitoring Committee
ECG	electrocardiogram
eCRF	electronic Case Report Form
eGFR	Estimated Glomerular Filtration Rate
ET	Early Termination
FCS	fully conditional specification
GCR	gout chronic response
GCR20	gout chronic response – 20% reduction
GCR50	gout chronic response – 50% reduction
GCR70	gout chronic response – 70% reduction

This document is confidential.

Abbreviation	Description
HAQ	Health Assessment Questionnaire
HAQ-DI	Health Assessment Questionnaire – Disability Index
HEENT	head, eyes, ears, nose, throat
HLGT	High-Level Group Term
IMM	Immunomodulator
ICF	Informed Consent Form
ICH	International Committee on Harmonisation of Technical Requirements for Pharmaceuticals for Human Use
IgG	Immunoglobulin G
IP	InterPhalangeal joint
IR	infusion reaction
ITT	Intent-to-Treat
IV	intravenously
kg	kilogram
KM	Kaplan-Meier
lb	pound
LS	least squares mean
MACE	Major Adverse Cardiovascular Events
max	maximum
MCP	MetaCarpoPhalangeal joints
MDRD	Modification of Diet in Renal Disease
MedDRA	Medical Dictionary for Regulatory Activities
mg	milligram
min	minimum
MITT	Modified Intent-to-Treat
mL	milliliter
mmHg	millimeters mercury
MMRM	mixed model repeated measures
MTP	MetaTarsophalangeal joints
MTX	methotrexate
MTX-PG(1-5)	methotrexate polyglutamate metabolites (1 through 5)
n	number of observations
NCS	not clinically significant
NIAID/FAAN	National Institute of Allergy and Infectious Diseases/Food Allergy and Anaphylaxis Network criteria
NSAID	non-steroidal anti-inflammatory drug

This document is confidential.

Abbreviation	Description
OMERACT	Outcome Measures in Rheumatology
PEG	polyethylene glycol
PIP	Proximal InterPhalangeal joints
PK	pharmacokinetics
PP	Per-protocol
PT	preferred term
RAMRIS	Rheumatoid Arthritis Magnetic Resonance Imaging scoring
Rx	prescription
SAE	serious adverse event
SAP	statistical analysis plan
SBP	systolic blood pressure
SD	standard deviation
SE	standard error
SMQ	Standardized MedDRA Query
SOC	System Organ Class
SOP	Standard Operating Procedure
sBLA	supplemental Biologic License Application
sUA	serum uric acid
TEAE	treatment emergent adverse event
TLF	Tables, Listings and Figures
TOEP	Toeplitz
TOEPH	heterogeneous Toeplitz
ULN	upper limit of normal range
ULT	urate lowering therapy
UN	unstructured variance-covariance matrix
VAS	visual analog scale
WHO	World Health Organization

This document is confidential.

## **2. Purpose**

The purpose of this statistical analysis plan (SAP) is to ensure that the data listings, summary tables and figures for the HZNP-KRY-202 study that will be produced, and the statistical methodologies that will be used, are complete and appropriate to allow valid conclusions regarding the study objectives.

### **2.1. Responsibilities**

██████████ will perform the statistical analyses and are responsible for the production and quality control of all tables, listings and figures (TLFs) for the HZNP-KRY-202 study, including summaries of concentrations for methotrexate (MTX) polyglutamate, pegloticase, and anti-drug antibodies (ADA). Additional pharmacokinetic (PK) analysis may be performed by a separate vendor and is not covered in the scope of this SAP.

██████████ will provide summarizations and listings for safety reviews.

### **2.2. Planned Analyses**

#### **2.2.1. Interim Analyses**

An external multidisciplinary Data Monitoring Committee (DMC) will review the progress of the study and perform review of unblinded, comparative efficacy and safety data in order to protect subject welfare and preserve study integrity. The scope of the analysis to be provided to the DMC is provided in a mutually agreed upon charter, which defines the DMC membership and meeting logistics.

There are two planned timepoints at which data will be reviewed by the DMC. The first analysis will occur after approximately half of the randomized subjects (i.e. ~78 subjects) have completed 24 weeks of treatment in the Pegloticase + Immunomodulator (IMM) Period or discontinued therapy (or study) prior to that time. The second unblinded, comparative analysis will be performed when all randomized subjects have completed 24 weeks of treatment or discontinued treatment (or study) prior to Week 24.

The main purpose of the analysis by the DMC is to review the safety data. However, limited efficacy data, including the primary efficacy endpoint, will be provided to the DMC for review to assist in assessing risk and benefit. Additionally, some data for the secondary endpoints (response during Month 12) will be included in the second analysis. Even though there is no plan to make an inference of the primary or secondary efficacy endpoints, an alpha adjustment of 0.0005 will be made to account for this analysis. The DMC will recommend to Horizon whether to continue the study with or without modification or stop the study due to safety reasons.

#### **2.2.2. Final Analysis**

The primary analysis of all endpoints will be performed after all subjects reach Week 52 in which the primary and secondary efficacy endpoints will be tested at the 0.0495 significance level in

This document is confidential.

sequential order. All other efficacy endpoints are exploratory in nature and will be tested using 2-sided tests at the 5% significance level without multiplicity adjustment.

A follow-up analysis will be performed after all subjects complete the post-treatment follow-up period. The follow-up analysis will only include descriptive summaries of the post-treatment efficacy and safety data.

In addition to the above analyses, blinded safety data will be summarized regularly throughout the study for safety monitoring by the Sponsor.

### **2.3. Coronavirus Disease 2019 (COVID-19)**

The COVID-19 pandemic outbreak occurred midway through enrollment for this study. This SAP will describe analyses to be performed to assess the impact of COVID-19 on the study and methods for handling missing data due to the effects of COVID-19 on study subjects and sites.

### **3. Study Objectives**

#### **3.1. Primary Objective**

The primary objective is to evaluate the effect of pegloticase with MTX vs. pegloticase with placebo for MTX on the response rate during Month 6 (Weeks 20, 21, 22, 23 and 24), as measured by the sustained normalization of serum uric acid (sUA) to <6 mg/dL for at least 80% of the time during Month 6.

#### **3.2. Secondary Objectives**

- Evaluate the effect of pegloticase with MTX vs. pegloticase with placebo for MTX on the response rate during Month 12 (Weeks 48, 50, and 52), as measured by the sustained normalization of sUA to <6 mg/dL for at least 80% of the time during Month 12.
- Evaluate the effect of pegloticase with MTX vs. pegloticase with placebo for MTX on the complete resolution of  $\geq 1$  tophi (using digital photography) at Week 52 in subjects with tophi at baseline.
- Evaluate the effect of pegloticase and MTX vs. pegloticase and placebo for MTX on the mean change from baseline in Health Assessment Questionnaire – Disability Index (HAQ-DI) Score at Week 52.
- Evaluate the effect of pegloticase with MTX vs. pegloticase with placebo for MTX on the mean change from baseline in Health Assessment Questionnaire (HAQ) Pain Score at Week 52.
- Evaluate the effect of pegloticase with MTX vs. pegloticase with placebo for MTX on the mean change from baseline in HAQ Health Score at Week 52.

#### **3.3. Exploratory Objectives**

- Evaluate the effect of pegloticase with MTX vs. pegloticase with placebo for MTX on the mean change from baseline in urate volume and bone erosions due to gout to Weeks 14, 24, and 52 based on dual-energy computed tomography (DECT).
- Evaluate the effect of pegloticase with MTX vs. pegloticase with placebo for MTX on the mean change from baseline in bone erosions due to gout to Weeks 24 and 52 based on X-rays of the hands and feet.
- Evaluate the effect of pegloticase with MTX vs. pegloticase with placebo for MTX on the complete resolution of  $\geq 1$  tophi (using digital photography) at Weeks 24 and 36 in subjects with tophi at baseline.
- Evaluate the effect of pegloticase with MTX vs. pegloticase with placebo for MTX on the mean change from baseline in tophus size (long axis measured using digital photography) to Weeks 14, 24, 36 and 52 in subjects with tophus present at baseline.
- Evaluate the effect of pegloticase with MTX vs. pegloticase with placebo for MTX on the

*This document is confidential.*

response rate during Month 9 (Weeks 32, 34, and 36), as measured by the sustained normalization of sUA to <6 mg/dL for at least 80% of the time during Month 9.

- Evaluate the effect of pegloticase with MTX vs. pegloticase with placebo for MTX on the response rate during Month 3 (Weeks 10, 12 and 14), as measured by the sustained normalization of sUA to <6 mg/dL for at least 80% of the time during Month 3.
- Evaluate the effect of pegloticase with MTX vs. pegloticase with placebo for MTX on the overall response rate, as measured by the sustained normalization of sUA to <6 mg/dL for at least 80% of the time during Month 3 (Weeks 10, 12, and 14) and Month 6 (Weeks 20, 21, 22, 23, and 24) combined.
- Evaluate the effect of pegloticase with MTX vs. pegloticase with placebo for MTX on reducing sUA to < 5 mg/dL for at least 80% of the time during Months 3, 6, 9 and 12, individually.
- Evaluate the effect of pegloticase with MTX vs. pegloticase with placebo for MTX on the mean change from baseline in sUA at Weeks 14, 24, 36 and 52.
- Evaluate the effect of pegloticase with MTX vs. pegloticase with placebo for MTX on the time to first sUA > 6 mg/dL.
- Evaluate the effect of pegloticase with MTX vs. pegloticase with placebo for MTX on the percentage of non-hyperuricemic (sUA < 6 mg/dL) time during Months 3, 6, 9 and 12.
- Evaluate the effect of pegloticase with MTX vs. pegloticase with placebo for MTX on the mean change from baseline in Health Assessment Questionnaire (HAQ) Pain Score at Weeks 14, 24, and 36.
- Evaluate the effect of pegloticase with MTX vs. pegloticase with placebo for MTX on the mean change from baseline in HAQ Health Score at Weeks 14, 24, and 36.
- Evaluate the effect of pegloticase and MTX vs. pegloticase and placebo for MTX on the mean change from baseline in Health Assessment Questionnaire – Disability Index (HAQ-DI) Score at Weeks 14, 24, and 36.
- Evaluate the effect of pegloticase with MTX vs. pegloticase with placebo for MTX on the mean change from baseline in tender joint count (68-point scale) at Weeks 14, 24, 36 and 52.
- Evaluate the effect of pegloticase with MTX vs. pegloticase with placebo for MTX on the mean change from baseline in swollen joint count (66-point scale) at Weeks 14, 24, 36 and 52.
- Evaluate the effect of pegloticase with MTX vs. pegloticase with placebo for MTX on the mean change from baseline in number of tender or swollen joints at Weeks 14, 24, 36 and 52.

This document is confidential.

- Evaluate the effect of pegloticase with MTX vs. pegloticase with placebo for MTX on the mean change from baseline in physician global assessment of gout at Weeks 14, 24, 36 and 52.
- Evaluate the effect of pegloticase with MTX vs. pegloticase with placebo for MTX on the proportion of subjects achieving 20%, 50%, or 70% improvement based on gout chronic response criteria at Weeks 14, 24, 36 and 52.
- Evaluate the effect of pegloticase with MTX vs. pegloticase with placebo for MTX on the mean change from baseline in systolic blood pressure (SBP) and diastolic blood pressure (DBP) to each visit.
- Assess the PK of pegloticase.
- Assess the MTX polyglutamate concentrations.
- Assess the incidence of anti-polyethylene glycol (PEG) and anti-uricase immunoglobulin (IgG) antibodies.

### **3.4. Safety and Tolerability Objectives**

- Evaluate the safety and tolerability of pegloticase with MTX vs. pegloticase with placebo for MTX by examining the following:
  - Adverse event (AE)/serious adverse event (SAE) profile overall for pegloticase and the combination of pegloticase and MTX
    - And in particular, the Incidence of adverse event of special interest (AESI): infusion reactions (IRs), anaphylaxis, gout flares, cardiovascular events
  - Mean change in laboratory results
  - Mean change in vital sign parameters

### **3.5. Brief Description**

This is a Phase 4, multicenter, randomized, double-blind, placebo-controlled, parallel-group study to evaluate the efficacy and safety of pegloticase with MTX vs. pegloticase with placebo for MTX in treating adult subjects with uncontrolled gout.

The study design will include: 1) Screening Period (screening should be completed within 4-6 weeks prior to Week -6); 2) 2-week MTX Tolerability Assessment Period consisting of 2 weeks of open-label oral MTX for all subjects; 3) Run-in Period consisting of randomization followed by 4 weeks of blinded oral MTX or placebo for MTX; 4) 52-week Pegloticase + IMM Period; 5) 30-day Safety Follow-up (Phone/Email/Site Visit) and 6) 3 and 6 month Post Treatment Follow-up.

All subjects who meet eligibility criteria at Screening will begin weekly 15 mg MTX orally at the Week -6 visit. Subjects will also take folic acid 1 mg orally every day beginning during the MTX Tolerability Assessment Period (Week -6 to Week -4) and continuing until prior to the Week 52 Visit.

This document is confidential.

Subjects must be able to tolerate the weekly dose of MTX 15 mg for 2 weeks to be eligible to be randomized at Week -4. Subjects who are unable to tolerate the 15 mg dose of MTX during the 2 weeks preceding the Week -4 visit during the Run-in Period will be considered screen failures.

Subjects who tolerate the weekly 15 mg MTX dose during the 2 weeks preceding Week -4 Visit and continue to meet eligibility criteria will be randomized at the Week -4 Visit in a 2:1 ratio (stratified by presence of tophi) to receive either blinded oral 15 mg MTX or blinded oral placebo for MTX. Tophi presence (yes, no) will be based on presence of at least one tophus identified by the Investigator. Subjects will continue to take the blinded MTX or placebo for MTX from Week -4 to Day 1 (the Run-in Period) at the 15 mg MTX or placebo for MTX dose. If a subject does not tolerate the 15 mg MTX or placebo for MTX dose after randomization at the Week -4 Visit and prior to Day 1, the MTX or placebo for MTX may be dose-reduced or discontinued based on pre-specified criteria and after discussion with the Sponsor medical monitor. The subject will be allowed to remain in the study. After Day 1, MTX or placebo for MTX may be re-initiated. The subject will be re-initiated to the same treatment they were randomized to at Week -4. The re-initiated MTX or placebo for MTX will remain blinded.

All subjects who complete the Run-in Period will receive the first pegloticase infusion on Day 1. All subsequent doses and study visits will be scheduled based on the Day 1 visit date.

It is required that before a subject begins the pegloticase + IMM Period, he or she has been taking at least one protocol standard gout flare prophylaxis regimen (i.e. colchicine and/or non-steroidal anti-inflammatory drugs and/or low-dose prednisone  $\leq 10$  mg/day) for  $\geq 1$  week before the first dose of pegloticase and continues flare prophylaxis per American College of Rheumatology guidelines [Khanna D et al. 2012] for the greater of 1) 6 months, 2) 3 months after achieving target serum urate (sUA  $< 6$  mg/dL) for patients with no tophi detected on physical exam, or 3) 6 months after achieving target serum urate (sUA  $< 5$  mg/dL) for patients with one or more tophi detected on initial physical exam that have since resolved. For IR prophylaxis, fexofenadine (180 mg orally) will be taken the day before each infusion; fexofenadine (180 mg orally) and acetaminophen (1000 mg orally) will be taken the morning of each infusion; and methylprednisolone (125 mg IV) given over an infusion duration between 10 - 30 minutes, initiated immediately prior to each infusion.

During the Pegloticase + IMM Period, pegloticase 8 mg will be administered intravenously (IV) every 2 weeks from Day 1 through the Week 50 Visit for a total of 26 infusions; pegloticase will be administered after all pre-dose study visit assessments have been completed at each visit. The date and start and stop time of infusion will be recorded. Serum uric acid stopping rules will be applied: subjects with sUA level  $> 6$  mg/dL at 2 consecutive study visits beginning with the Week 2 Visit will discontinue treatment, complete the End of Pegloticase Infusion Visit procedures within 2 weeks and continue the subject visits according to the protocol (without treatment).

During the Pegloticase + IMM Period, subjects will be instructed to take MTX or placebo for MTX weekly on the same day each week, within 1 to 3 days prior to each pegloticase infusion and one additional weekly dose after the last infusion for subjects who have not stopped pegloticase due to sUA stopping rules; however, if a subject does not do so, MTX or placebo for MTX must be taken  $\geq 60$  minutes prior to each pegloticase infusion.

After Day 1, if a subject becomes unable to tolerate MTX or placebo for MTX, the MTX or placebo for MTX dose may be reduced and/or discontinued based on pre-defined criteria, and the subject may remain in the study.

After the Week 52 Visit (or End of Pegloticase Infusion Visit [if applicable]), subjects should resume regular care for gout per the judgment of the treating physician, including resumption of urate lowering therapy (ULT) upon pegloticase discontinuation, if appropriate. Subjects will have a 3 and 6 Month Follow-up visit to assess clinical status, including sUA levels.

Subjects who receive at least one dose of MTX or placebo for MTX and are females of childbearing potential will receive a safety follow-up phone call/e-mail approximately 30 days after the last dose of MTX or placebo for MTX to verify at least one ovulatory cycle has occurred after the last dose of MTX or placebo for MTX. If the subject has not ovulated, a urine pregnancy test will be performed. Subjects who receive at least one dose of MTX or placebo for MTX and who are non-vasectomized males, will be asked, 3 months after MTX or placebo for MTX discontinuation, regarding partner pregnancy.

Safety assessments, including monitoring and recording of all AEs, whether or not drug-related, measurement of vital signs, physical examinations, and monitoring of hematology and blood chemistry, will be performed.

An external DMC will be convened to review data for safety and efficacy with the timepoint of review and criteria outlined in the DMC Charter, with the possibility of DMC recommendation on study cessation or study design modification per criteria also to be outlined in the Charter.

An independent external adjudication committee will review reported events of infusion reactions, cardiovascular events and anaphylaxis.

### **3.6. Determination of Sample Size**

The response rate during Month 6 on pegloticase 8 mg every 2 weeks was 43% for the phase 3 studies. A sample size of 135 subjects (90 subjects randomized to receive pegloticase with MTX, 45 subjects randomized to receive pegloticase with placebo for MTX) provides 88% power at the 2-sided alpha=0.05 level to detect a difference of 28% (71% response rate for pegloticase with MTX vs. 43% for pegloticase with placebo for MTX).

The COVID-19 pandemic outbreak occurred midway through enrollment for the study, which has affected some subject enrollment and data acquisition during the trial. As a result, the Sponsor has planned to enroll approximately 10 additional subjects (for a total of 145 randomized subjects), in order to obtain information equivalent to studying at least 135 subjects not impacted by COVID-19.

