#### **9.3.4 Replacement Policy**

##### **9.3.4.1 Subjects**

In general, subjects that prematurely discontinue from the study for any reason will not be replaced. An exception may be made for subjects who are unevaluable due to the impact of the COVID-19 pandemic and associated restrictions on movement and work. Subjects unable to receive treatment or be evaluated due to restrictions during the COVID-19 pandemic may be replaced, at the

discretion of the sponsor. This may result in more subjects than originally planned being enrolled into the study to allow for the originally planned number to be evaluable for the primary efficacy analysis.

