### 6.3.3. Missing Data due to COVID-19 in sUA Responder Endpoints

In general, the estimand for this study will use the Treatment Policy Strategy for intercurrent events (ICEs), as planned during the design of this study. However, the COVID-19 pandemic was not anticipated, and the methodology will be changed for some ICEs. To make the analysis results applicable to the post-pandemic situation in which the virus is present in society but site closures (due to COVID-19) do not prevent office visits, subjects missing primary and secondary endpoint data due to site closure related to COVID-19 will have missing data addressed using the Hypothetical Strategy for ICEs. Under this strategy, partial data will be used for more efficient estimates of the analysis parameters.

The protocol deviation eCRF and disposition eCRFs will record reasons for missed visits, interruptions in study treatment, and reasons for treatment discontinuation. For deviations related to COVID-19, the study team will review before database lock and unblinding and assign a category for missing data as defined below. For analyses of response during a timepoint (Month 3, Month 6, Month 9, and Month 12), the following rules will be applied:

- Stopping rule: if a subject meets the sUA stopping rule prior to the analysis timepoint of interest and prior to any other COVID-19 impact (from categories below), the subject will be considered a non-responder for any timepoint after stopping rule was met.
- COVID-19 infection: if a subject is missing results during the timepoint due to confirmed or suspected COVID-19 infection prior to this period the subject will be considered a non-responder.
- Site closure: if a subject is ongoing in the study but the site is closed due to COVID-19 during the analysis timepoint of interest, resulting in missing data for the timepoint, then multiple imputation will be used to impute missing sUA values during the timepoint to calculate response.
- COVID-19 related: if a subject has missing data for the analysis timepoint of interest due to COVID-19 (e.g. had concerns about remaining in study due to pandemic, sheltering in place/unable to travel due to COVID-19 restrictions) then the subject will be considered a non-responder.

Details of the multiple imputation process are described in Section [9.2.2](#)

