### **9.2. Primary Efficacy Endpoint and Analysis**

This study will compare pegloticase 8 mg co-administered with MTX to pegloticase 8 mg co-administered with placebo in subjects with uncontrolled gout. The primary efficacy endpoint is the proportion of Month 6 (Weeks 20, 21, 22, 23, and 24) responders, defined as subjects achieving and maintaining sUA < 6 mg/dL for at least 80% of the time during Month 6. The objective is to demonstrate superiority of pegloticase given with MTX over pegloticase given with placebo. The primary comparison will be made for ITT population, i.e., all randomized subjects, regardless of adherence to study treatment. The comparison is between randomized (planned) treatment groups of pegloticase given with MTX over pegloticase given with placebo.

[figure not shown]

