### 9.2.2. Handling of Missing Data and Multiple Imputation Process

At least two sUA observations from different visits during Month 6 must be available in order for a subject to be eligible for consideration as a responder. Subjects with only one sUA observation will be considered non-responders, regardless of the value of that single observation; subjects with no sUA values will also be considered non-responders. In addition, subjects who meet the stopping rule (sUA values > 6 mg/dL at 2 consecutive scheduled visits (excluding post-infusion sUA) starting at Week 2 prior to or during Month 6 will be considered to be non-responders. For determination of stopping rule, as specified in Section 9.1, if both central lab and local lab sUA results are available at a visit then the central lab value will be used for stopping rule determination. For subjects with missing data due to COVID-19 that is not “Site Closure”, there will be no imputation of sUA values due to missing values among those collected between Week 20 and Week 24.

For subjects with missing data due to site closure (due to COVID-19 as defined in Section 6.3.3) during Month 6 (i.e. have < 2 visits during Month 6 with sUA available), multiple imputation will be used to impute missing sUA values .

The multiple imputation process for imputing missing sUA will involve the following steps:

- 1) For subjects who met the stopping rule and have missing data prior to or during Month 6, last observation carried forward (LOCF) imputation will be done in order to prevent the

This document is confidential.

multiple imputation algorithm from imputing data inconsistent with known information. For example, subjects who meet the sUA stopping rule and have missing sUA after stopping rule is met would be expected to continue to have sUA > 6 mg/dL in the absence of other treatment, and thus would be expected to be non-responders. LOCF is used to provide complete data for stopping rule subjects that may be used to impute missing sUA for "Site Closure" subjects. Note that these LOCF values will only be used in the imputation model, and will be excluded from all analyses once the imputation model has been used.

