### 9.2.5. Sensitivity Analysis of the Primary Endpoint

The following sensitivity analyses of the primary efficacy analysis will be performed for the ITT Population:

- 1) Include sUA results (if available) in the response calculation following discontinuation of treatment for subjects who meet stopping rule and continue on the study (i.e. will not automatically assign non-response if stopping rules met).
- 2) Exclude sUA results (treat as missing) after the start of the urate lowering therapy taken after the first dose of pegloticase if subjects receive urate lowering therapy other than pegloticase.
- 3) Exclude all subjects from analysis with “COVID-19 Related” or “Site Closure” (per Section 6.3.3) missing data during Month 6.
- 4) Impute non-response for “Site Closure” subjects in the pegloticase with MTX group and impute response for “Site Closure” subjects in the pegloticase with PBO group (i.e. a worst-case analysis).
- 5) If multiple imputation is performed, a tipping point analysis will be performed to evaluate the robustness of the primary analysis to the missing at random (MAR) assumptions. First, all missing data will be imputed by the FCS method described in Section 9.2.2. Then, a small adjustment value will be added to the imputed values during Month 6 for the pegloticase + MTX group in each of the 100 datasets. Response will be calculated based on the adjusted imputed sUA values for “Site Closure” subjects and observed sUA values for all other subjects, and pooled together using Rubin’s rule to get a p-value. This process is repeated with a more stringent adjustment until the p-value > 0.0495.

Sensitivity analyses 1 and 2 above will be performed with the same statistical method used in primary analysis of the primary endpoint, including use of multiple imputation (if performed for primary analysis). Sensitivity analyses 3 and 4 will be performed with the same statistical method used in the primary analysis of the primary endpoint but will not apply the multiple imputation process.

As specified in Section 9.2.2, subjects are required to have at least two sUA results from different visits during Month 6 in order to be eligible for consideration as a responder. Post-hoc analysis may be performed in which this requirement is removed, and in the event that only a single sUA result is available during Month 6, response will be determined based on the value of the sUA result (e.g. if sUA < 6 mg/dL then the subject is a responder).

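### Does going from 135 to 145 subjects fail to protect power, given that two kinds of COVID-19 missing data are scored as non-response?

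*SAP*

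**What the plan says.** SAP 3.6 gives 88% power for 135 subjects (90 and 45) at two-sided 0.05, for 71% against 43%. It then plans about 10 more, 145 in all, "in order to obtain information equivalent to studying at least 135 subjects not impacted by COVID-19". Protocol 9.3.4.1 allows replacement of subjects affected by the pandemic with a similar purpose: "to allow for the originally planned number to be evaluable for the primary efficacy analysis".

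SAP 6.3.3 sorts COVID-19 missing data into categories. Site closure leads to multiple imputation. A subject "missing results during the timepoint due to confirmed or suspected COVID-19 infection prior to this period the subject will be considered a non-responder". The remaining COVID-19 reasons are treated the same way: "sheltering in place/unable to travel due to COVID-19 restrictions) then the subject will be considered a non-responder". The primary comparison in SAP 9.2 takes "all randomized subjects, regardless of adherence to study treatment". SAP 9.2.2 requires sUA from at least two different Month 6 visits for a subject to be eligible as a responder, and outside site closure "subjects with no sUA values will also be considered non-responders". Sensitivity analysis 3 in SAP 9.2.5 does the opposite for two of the categories: "Exclude all subjects from analysis with" missing data that are COVID-19 related or due to site closure.

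**The concern.** Ten extra subjects replace ten affected ones exactly only if the affected ones leave the analysis. Here two of the categories stay in the denominator as failures. A failure scored in the MTX arm pulls that arm's rate down, and failures spread over both arms shrink the difference as well as costing information. The sentence in SAP 3.6 seems to describe sensitivity analysis 3 better than the primary analysis. It is also the SAP's stated reason for the increase, so a reader could take the 88% as protected against the pandemic when no calculation shows it. What is at stake is power, and the accuracy of one sentence about it.

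**Working it through.** **Inputs.** From SAP 3.6: 71% and 43%, arms of 90 and 45, total raised to 145. From SAP 2.2.2: final test level 0.0495. The 2:1 ratio makes 145 about 97 and 48. The number k scored as COVID-19 non-responders is not in the documents, so it is varied.

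**Formula.** Pooled two-proportion z-test: power = Φ[(d − z·SE₀)/SE₁]. Here d is the difference, SE₀ = √[p̄(1−p̄)(1/n₁+1/n₀)] and SE₁ = √[p₁(1−p₁)/n₁ + p₀(1−p₀)/n₀].

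**The plan's own figure.** p̄ = (63.9 + 19.35)/135 = 0.6167, SE₀ = 0.0888, SE₁ = 0.0879.
- At 0.05 (z = 1.960): (0.28 − 0.1740)/0.0879 = 1.206, power 88.6%. This reproduces the stated 88%.
- At 0.0495 (z = 1.964): power 88.5%. This is the reference below.

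**145 subjects, even spread.** Suppose the k cases fall in proportion to arm size and are unrelated to the outcome the subject would have had. Both rates are then multiplied by (1 − k/145). For k = 10 the factor is 0.931, the rates are 66.1% and 40.0%, d = 26.1 points, and power is Φ(1.045) = 85.2%.

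| k | Power at 0.0495 | Unaffected N with the same power |
|---|---|---|
| 0 | 90.5% | – |
| 4 | 88.5% | 135 |
| 5 | 88.0% | 133 |
| 8 | 86.3% | 126 |
| 10 | 85.2% | 122 |
| 15 | 82.1% | 112 |

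On this assumption the break-even is 4, and holding 88.5% at k = 10 would take about 158 randomized. If the ten were all site closures carrying no information, 145 would act as 135 and power would be about 88.5%.

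**Whole subjects.** The even spread uses fractions: at k = 4 it puts about 2.7 cases in the MTX arm and 1.3 in the placebo arm. With integers, multiplying each arm's rate by its own factor (for 3 MTX cases, 0.71 × 94/97 = 0.688):

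| MTX + placebo | k | Power | Against 88.5% |
|---|---|---|---|
| 2 + 0 | 2 | 87.0% | below |
| 3 + 1 | 4 | 87.2% | below |
| 3 + 2 | 5 | 89.3% | above |
| 4 + 3 | 7 | 89.6% | above |

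So 2 can fail and 7 can pass. If only would-be responders can be scored this way, at the same rate in both arms, the limit falls to 2 (88.9% at k = 2, 88.1% at k = 3). If all cases fall in the MTX arm it is 1. Placebo-heavy splits raise the figure only by lowering the control rate, which is bias and not information.

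**Information read as precision.** SAP 3.6 does not define information as power. The inverse variance of the risk difference for 135 unaffected subjects is 1/(0.71×0.29/90 + 0.43×0.57/45) = 129.3. For 145 with k = 10 evenly spread it is 136.8. On that reading the aim is met even at ten, and what remains is dilution of the difference.

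**The case for a change.** The case for rewording runs as follows. The equivalence is stated without a calculation, it does not follow from the rules in SAP 6.3.3, and it fails on a neutral assumption once 5 of 145 (3.4%) are scored as failures. The cost would be a sentence or two of SAP text. The team must in any case assign the categories before database lock and unblinding, so the counts will exist.

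The core of this stands: the equivalence is conditional, and SAP 3.6 does not say so. Three things weaken it as a reason to act. First, the shortfall at 5 is half a point, below the precision at which the SAP quotes power and within what an increase of approximately ten can claim. Second, being affected by COVID-19 is far from being scored a COVID-19 non-responder. Month 6 has five visits, two with sUA suffice for eligibility, and a local result stands in when the central one is missing (SAP 9.1). Nothing in the documents shows the count reaching 5. Third, a stated limit of 4 would be more precise than the plan supports, as the integer splits show.

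A side point is the first interim look, placed at "approximately half of the randomized subjects (i.e. ~78 subjects" in SAP 2.2.1 and at the same number in Protocol 9.6.8. Half of 135 is 67.5 and half of 145 is 72.5, so the number fits neither total. This is a clerical slip. The 0.0005 set aside does not depend on it, and no efficacy inference is planned at that look.

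**Conclusion.** No change follows. SAP 3.6 states an aim for enrolment and leaves out the assumed number affected. That is missing detail, and no analysis depends on it. The 88% for 135 subjects is right.

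Scoring COVID-19 missing data as failure is a fair, conservative choice. It is fixed in advance, categories are assigned blind, and if it falls alike on both arms it does not inflate the error rate under the null. Its price is some dilution: about 3 points of power (88.5% to 85.2%) if ten evenly spread subjects were scored this way, and nothing at four or fewer. Those figures assume 71% and 43%, a 97/48 split, a pooled z-test at 0.0495 and cases unrelated to outcome. The break-even ranges from about 1 to 5, or more if placebo-heavy.

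The plan already lets a reader see the effect. COVID-19 deviations are summarised and listed (SAP 5.7) and discontinuations due to COVID-19 counted (SAP 7). Sensitivity analyses 3 and 4 handle the missing data differently, and subjects randomized after the 135th form a prespecified subgroup for the primary endpoint (SAP 6.6). After the trial, the confidence interval shows the precision obtained, whatever SAP 3.6 said. A conditional power table would add nothing to that.
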